8.2.4. Sensitivity analysis

For all secondary analysis of body weight and SBP, missing data will be imputed via multiple imputations, following which the MMRM will be repeated on the complete datasets with results combined across complete datasets using standard multiple imputations techniques; Values collected after the start of rescue medication will be considered missing. Imputation steps include:

- a. Create monotone missing data as step a of section 8.1.1 with 100 imputed datasets;
- b. Regression approach under MAR will be used to generate complete datasets. The predictors for the regression imputation model at any time point will be region, treatment background (metformin only or metformin and OHA), baseline eGRF (≥ 90 or < 90 ml/min/1.73 m²), treatment, and values at all previous time points, including baseline. Values at each visit will be imputed sequentially. The first imputed values for subjects in bexagliflozin arm will be penalized by the mean improvement at week 60 on that endpoint (i.e. the mean change from baseline at week 60). Imputed values for subjects in glimepiride will not be penalized. Imputed values after the first missing value will be penalized through regression on first penalized value.
- c. Imputed datasets will be analyzed and results combined as in step c in section 8.1.1.

For the sensitivity analyses of proportion of subjects with hypoglycemia event, to account for subject discontinuation, incidence rate will be analyzed using negative binomial regression model. Data collected after the start of rescue medication will be considered as missing. The number of severe or documented symptomatic

hypoglycemia events will be used as outcome. Model will include region, treatment background (metformin only or metformin and OHA), baseline eGRF (≥ 90 or < 90 ml/min/1.73 m²), treatment, and baseline HbA_{1c} as fixed effect and the logarithm of the duration from first dose of double-blind treatment to date of week 96 visit as offset. If subject discontinued before week 96 visit, the date of discontinuation will be used. If subject used rescue medication, the last date before rescue medication will be used. The adjusted mean incidence over 96 weeks, 95% CI for each treatment arm, the risk ratio, 95% CI, and p-value will be presented.

8.3. EXPLORATORY EFFICACY ENDPOINTS AND ANALYSES

All endpoints in this section are exploratory. No sensitivity analysis and adjustment for multiple comparisons will be conducted. Nominal p-values will be used to examine any trends in these endpoints.

8.3.1. Changes from baseline in HbA_{1c}, body weight, SBP, and in FPG over time

The schedule of HbA_{1c}, FPG, body weight, and SBP/DBP can be found in Table 1. The absolute value and change from baseline in HbA_{1c}, FPG, body weight and SBP/DBP during the double-blind treatment period will be summarized by descriptive statistics at each visit. Change from baseline in HbA_{1c} will be analyzed as part of primary efficacy analysis. The change from baseline in body weight for subjects with baseline BMI ≥ 25 kg/m², SBP for subject with baseline SBP ≥ 140 mmHg, SBP for all subjects, and FPG will be analyzed using the MMRM ANCOVA model from primary analysis as a template (Section 8.1.1). The fixed effect for change from baseline in body weight and SBP will include region, baseline HbA_{1c} as continuous variable, treatment background (metformin-only or metformin-and-OHA), and baseline eGFR (≥ 90 or < 90 mL/min/1.73 m²), treatment, visit, and treatment-by-visit. The change from baseline in FPG will include region, treatment background (metformin-only or metformin-and-OHA), and baseline eGFR (≥ 90 or < 90 mL/min/1.73 m²), treatment, visit, and treatment-by-visit. The appropriate baseline values will be used as covariate. LS means for each treatment and the difference between treatments will be estimated at each visit and across all post-baseline visits. The corresponding p-values will also be presented.

8.3.2. Proportions of subjects with HbA_{1c} of $< 7\%$ and the proportion of subjects with ≥ 1 severe or documented symptomatic hypoglycemia events over time

Summary on the proportion of subjects achieving HbA_{1c} $< 7\%$ at each visit and the proportion of subjects with documented hypoglycemia event during each 12-week visit interval will be presented over time. They will be analyzed using generalized estimating equation (GEE) logistic regression. The fixed effect will include region, treatment background (metformin-only or metformin-and-OHA), baseline eGFR (≥ 90 or

< 90 mL/min/1.73 m²) and baseline HbA_{1c}, treatment, visit, and treatment-by-visit. An unstructured correlation structure will be used (or autoregressive(1) if the model with the unstructured structure does not converge). The LS mean proportion for each treatment will be estimated at each post-baseline visit and across all post-baseline visits. The odds ratios of bexagliflozin group over the glimepiride group at each visit and across all post-baseline time points will be estimated from LS means based on the model with the corresponding p-values and their two-sided 95 % CIs presented. Sample SAS code will be provided in Appendix.

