3.9. TREATMENT ASSIGNMENT & BLINDING

3.9.1. Treatment Assignment

The study will be conducted at multiple investigative sites and will likely involve various numbers of subjects at each site. The study will have a competitive enrollment but the number of randomized subjects from each site will be capped at 40. Activation of investigational sites will be centrally controlled by an Interactive Web Response System (IWRS). Subject randomization will be deactivated for all sites when the planned number of subjects is met. However, if a potential subject is in wash-out already and wishes to continue with the study, the subject will be allowed to continue and, if eligible, to be randomized.

Eligible subjects who have completed the wash-out of oral hypoglycemic agent other than metformin and have met all study inclusion/exclusion requirements are to be randomized in a 1:1 ratio to receive active bexagliflozin with placebo glimepiride or active glimepiride with placebo bexagliflozin. Subjects will be assigned to treatment groups in sequential order as they qualify for the study. Randomization will be stratified according to baseline (Visit V5) HbA_{1c} (< 8.5% or ≥ 8.5%), treatment background

(metformin-only or metformin-and-OHA), and Visit V5 eGFR (≥ 90 or < 90 and ≥ 60 mL/min/1.73 m²).

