13. CHANGE FROM ANALYSIS PLANNED IN PROTOCOL

In all analysis models, continuous HbA_{1c} at baseline is used as fixed effect, in place of randomization stratification factor of HbA_{1c} group at baseline. In all models, eGFR at baseline category is used as fixed effect, in place of randomization stratification factor of eGFR at screening.

Primary analysis of the primary endpoint was MMRM using available data in the protocol. In SAP, a “retrieved dropout” analysis is used for handling missing data is used as primary analysis if data allows. Retrieve dropouts are subjects who discontinued treatment but still had their efficacy measurements at the planned visit. Sensitivity analysis of LOCF is planned in the protocol, but removed in SAP since LOCF does not add more information on sensitivity in addition to tipping point analysis.

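### The FPG model in SAP 8.3.1 omits baseline HbA1c, contrary to the SAP's own rule for all models, and so leaves a stratification factor unadjusted

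*SAP*

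**What the plan says.** SAP 8.3.1 analyses FPG over time with a repeated-measures model patterned on the primary one and then lists the terms by endpoint.

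- Body weight and SBP: "The fixed effect for change from baseline in body weight and SBP will include region, baseline HbA_{1c} as continuous variable", followed by treatment background, eGFR category, treatment, visit and treatment-by-visit.
- FPG: "The change from baseline in FPG will include region, treatment background", followed by baseline eGFR category, treatment, visit and treatment-by-visit. HbA1c does not appear.
- All these endpoints: "The appropriate baseline values will be used as covariate".

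SAP section 13, on changes from the protocol, states: "In all analysis models, continuous HbA_{1c} at baseline is used as fixed effect, in place of randomization stratification factor of HbA_{1c} group at baseline". It mentions no endpoint as an exception.

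SAP 3.9.1 gives the design: "Randomization will be stratified according to baseline (Visit V5) HbA_{1c} (< 8.5% or ≥ 8.5%), treatment background" and eGFR. Protocol 3.3.2 and 5.4 also name HbA1c at Visit V5 as a stratification factor. Protocol 9.7 allows an FPG model similar to the primary MMRM, and Protocol 9.5.2 puts the stratification factors in that model.

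**The concern.** A programmer who follows SAP 8.3.1 to the letter fits FPG without baseline HbA1c; one who follows section 13 includes it. FPG over time is a stated exploratory objective with its own table and figure (both numbered 14.2.5) and model-based p-values, so one model should be fixed in advance.

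The version in 8.3.1 also breaks the link between design and analysis. Randomisation was balanced on three factors. The FPG model keeps treatment background and eGFR (as the baseline category that section 13 substitutes), but has neither the HbA1c stratum nor its continuous replacement. When a model leaves out a prognostic stratification factor, its standard error does not credit the balance that stratification produced, and the interval is somewhat wider than it need be.

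**Working it through.** **1. Can the text of 8.3.1 be read as including HbA1c?** The closing sentence on baseline covariates applies to weight, SBP and FPG alike. For weight and SBP it supplies the endpoint's own baseline, because HbA1c is named separately for them. By the same construction it supplies baseline FPG for FPG, and nothing more. The reference to the primary model as a template does not restore HbA1c either: there HbA1c is the outcome's own baseline, and an explicit term list follows for each endpoint.

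**2. Is FPG the only exception?** Baseline HbA1c by outcome model:

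| Model | SAP section | Baseline HbA1c |
|---|---|---|
| HbA1c, primary MMRM | 8.1.1 | yes |
| Body weight | 8.2.1, 8.3.1 | yes |
| SBP | 8.2.2, 8.3.1 | yes |
| Hypoglycemia, logistic | 8.2.3 | yes |
| Hypoglycemia, negative binomial | 8.2.4 | yes |
| Responder and hypoglycemia GEE | 8.3.2 | yes |
| EQ-5D-3L | 10 | yes |
| FPG | 8.3.1 | **no** |

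The imputation regressions for weight and SBP in 8.2.4 do not name it either, but they are not outcome models and are left aside.

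**3. Sample size for the check.** The plan gives no figure for FPG. Its evaluable number per arm reproduces: 2 × (1.960 + 1.282)² × (1.0/0.35)² = 171.6, so 172; and 172/0.82 = 209.8, so 210. Neither number depends on the FPG model.

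**4. Precision.** Let r be the partial correlation of baseline HbA1c with FPG change, given baseline FPG. The documents give no value, so r is an assumption. Adding HbA1c multiplies the residual SD, and so approximately the model standard error, by √(1 − r²).

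| r (assumed) | SE excess without HbA1c, 1/√(1 − r²) − 1 | SE fall if added, 1 − √(1 − r²) |
|---|---|---|
| 0 | 0% | 0% |
| 0.1 | 0.5% | 0.5% |
| 0.2 | 2.1% | 2.0% |
| 0.3 | 4.8% | 4.6% |
| 0.4 | 9.1% | 8.3% |

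**5. Which r is plausible?** Take a simple stationary model in which both measures are noisy readings of one latent glycemia: FPG reliability a, HbA1c reliability b, persistence ρ from baseline to follow-up. Then

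r² = ρ²ab(1 − a)² / [(1 − a²ρ²)(1 − ab)].

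With assumed ranges a = 0.5 to 0.7, b = 0.6 to 0.8 and ρ = 0.4 to 0.6:

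- Low end (a = 0.7, b = 0.6, ρ = 0.4): 0.006048/(0.9216 × 0.58) = 0.0113, so r = 0.11 and the SE falls 0.6%.
- High end (a = 0.5, b = 0.8, ρ = 0.6): 0.036/(0.91 × 0.60) = 0.0659, so r = 0.26 and the SE falls 3.4%.

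That is 1.1% to 6.6% of residual variance, inside the r = 0 to 0.3 rows above.

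**6. Validity.** Simulation with 172 per arm, permuted blocks within the two HbA1c strata, no true effect, one follow-up time and 4,000 trials per row:

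| r | Two-sided type I error without HbA1c | With HbA1c |
|---|---|---|
| 0 | 5.5% | 5.6% |
| 0.2 | 5.0% | 5.3% |
| 0.4 | 3.9% | 4.8% |

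The Monte Carlo error of each rate is about √(0.05 × 0.95/4000) = 0.34 percentage points. Mean estimates were within 0.004 of zero, against standard errors of about 0.10. At r = 0.4 without HbA1c, the model standard error averaged 0.108 while the estimates' actual SD was 0.103: the interval is too wide, not too narrow.

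**The case against.** The strongest reply is that this is a wording gap. A term list need not be exhaustive, and the general rule in section 13 could simply add HbA1c to it. That reading is weakened by the adjacent sentence, which names HbA1c for weight and SBP and would not need to if section 13 supplied it everywhere. The ambiguity stands, and removing it is the purpose of the point.

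A second reply is that the omission may be deliberate: FPG is itself a glycemic measure and keeps its own baseline. That is a recognisable choice, and listing FPG as an exception in section 13 would make the SAP consistent. But the SAP gives no such reason, and overlap between two baseline covariates does not harm the estimate of a randomised treatment effect.

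A third reply is about importance, and it stands. SAP 8.3 makes every endpoint in it exploratory with nominal p-values. Protocol 9.1 describes exploratory objectives as descriptive, and Protocol 9.7 makes the FPG model optional.

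Two stronger readings are tempting and not supported:

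- A reader might infer that HbA1c should be added because it measures baseline glycemia more stably than one fasting value. The documents give no reliability for either. Protocol 6.18 says HbA1c reflects 2 to 3 months, while subjects on a second agent stop it 8 weeks before randomisation and V5 falls 3 to 5 days before it, so about 51 to 53 days after stopping. Their V5 HbA1c may still partly reflect the withdrawn drug.
- A reader might infer that the FPG result would be biased or its error rate inflated. The check shows neither.

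**Conclusion.** The contradiction is real: SAP 8.3.1 specifies an FPG model that SAP section 13 rules out, and that model is unadjusted for HbA1c, a randomisation stratification factor. The case for adding HbA1c rests on consistency with the SAP's own rule and with the stratified design.

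The size is small. The standard error would fall by 0 to about 5% for assumed r from 0 to 0.3; r = 0.4 would give 8.3%, but lies above the 0.11 to 0.26 implied by the latent-glycemia assumptions. All these values are assumptions, worked at a single follow-up time rather than in the full repeated-measures model. The treatment estimate is unbiased either way, and the test without HbA1c is at most mildly conservative. FPG is outside the testing hierarchy, so no confirmatory conclusion and no sample size figure changes. This is a minor improvement.

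**What to change.** In SAP 8.3.1, add continuous baseline HbA1c to the fixed effects for change in FPG, and name baseline FPG explicitly as the endpoint's own baseline covariate, so that the section agrees with section 13. Check the FPG table shell and any sample code against the revised list.

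The cost is a few words and one degree of freedom. No new data are needed: HbA1c between 7.0% and 10.5% at Visit V5 is an entry requirement, so every correctly randomised subject has the value. The change should be made before unblinding.

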9. SAFETY

The Safety Analysis Set will be used for analyzing the safety parameters. Safety data include AEs; physical examination results; vital signs; ECG results; and clinical laboratory results, including serum chemistry, hematology, serum lipids, and urinalysis.

Observed data will be summarized by treatment group as counts and percentages for discrete variables and means, standard deviations, medians, minimum, and maximum for continuous variables. All subjects who are randomized and receive at least one dose of double-blind study medication will be included in the safety analysis. All safety data will be presented in by-subject listings and included in the clinical trial report.

9.1. EXTENT OF EXPOSURE

Study drug exposure will include:

- Treatment duration by treatment group
- Total dose taken by treatment group

Treatment duration of tablets/capsules (in weeks) is calculated as (the date of the last dose of study drug - the date of the first dose of double-blind study drug + 1) / 7 and rounded to 1 decimal place. For glimepiride, this includes doses taken during up-titration period. The exposure will be summarized for bexagliflozin tablets, 20 mg or glimepiride, 2, 4, or 6 mg.

Total dose taken will be calculated as number of tablets/capsules dispensed - number of tablets/capsules, including all doses for glimepiride, returned. For unreturned bottles, if subject has completed the study, all study medications are considered as completely taken. If a subject withdrew early, and it is not the last kit dispensed, all medication will be considered as completely taken. If a subject withdrew early, and the last kit dispensed is not returned, the number taken is considered as what expected from date of dispense to the date of last dose date. Summary statistics for total dose taken will be provided by treatment group for the double-blind treatment period.

Summary statistics for treatment duration (in weeks) and a frequency summary of treatment duration categories (e.g., ≥ 1 Day, ≥ 6 weeks), will be provided.

9.2. TREATMENT COMPLIANCE

Subjects will be provided with dosing instructions each time study medication is dispensed. Subjects will also be instructed to bring their medication with them to every visit. During the run-in period, subjects will be considered compliant in investigational product administration by missing no more than two doses of run-in medication. Subjects who are not compliant during the run-in period will be excluded from randomization.

At each visit the study staff will review the self-monitored blood glucose (SMBG) control diary, glucometer data and medication use with the subject and record the drug consumption in the CRF. Reasons for non-adherence will also be recorded in the protocol deviation log if applicable.

Compliance in the double-blind phase is calculated for as follows:

- Percent compliance = (number of tablets or capsules taken / number of tablets should have taken) x 100.
- Number of tablets taken = number of tablets dispensed - number of tablets returned.
- Number of tablets should have taken = (number of tablets supposed to take in a day) x (number of exposure days).
- Number of exposure days = last dose date - first dose date + 1.

In case of the unreturned bottles:

- If subjects completed the study, all the unreturned bottles will be assumed to be completely consumed.
- If subjects discontinued, the unreturned bottles will be assumed to be completely consumed if a) unreturned bottles are not from the last visit, or b) if only one of the two bottles dispensed from week 60 or week 72 is not returned.
- If subjects discontinued and all bottles from the last visit are not returned (e.g. lost to follow-up), subjects will be assumed to consume the medication as expected:

Number of tablets assumed taken = last dose date - date bottles dispensed + 1;

Summary statistics for tablet or capsule compliance (%) will be provided by treatment group for the double-blind treatment period. The compliance will only be summarized for non-placebo tablets/capsule. A frequency summary of compliance will also be presented with the following categories: < 75%, 75% - < 100%, 100% - ≤ 120%, and > 120%.

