5.9.2 Bexagliflozin Kit

One bexagliflozin kit contains a bottle of 90 counts of bexagliflozin tablets, 20 mg or placebo.

The label attached to each bexagliflozin kit will contain the protocol number, product identification, kit number, batch number, expiration date, subject number, investigator name, storage condition, directions for use, sponsor's name and address, and the investigational drug caution statement.

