5.9.3 Glimepiride Kit

One glimepiride kit contains a 90 count bottle of one of the following products:

- Glimepiride capsules, 2 mg or placebo
- Glimepiride capsules, 4 mg or placebo
- Glimepiride capsules, 6 mg or placebo

The label attached to each glimepiride kit will contain the protocol number, product identification, kit number, batch number, expiration date, subject number, investigator name, storage condition, directions for use, sponsor's name and address, and the investigational drug caution statement.

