6.13 Dispensing Investigational Product

6.13.1 Dispensing Bexagliflozin

At randomization and at every 12 weeks of treatment thereafter, each study subject will receive 1 bottle of bexagliflozin tablets, 20 mg or placebo, based on the kit number assigned to the subject by the IWRS. At visit V15, two bottles of bexagliflozin tablets will be dispensed for dosing between week 72 and week 96.

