6.13.2 Dispensing Glimepiride

Weeks 0 to 6

- Each subject will receive 1 bottle of glimepiride capsules, 2 mg or placebo, at randomization.
- During weeks 2 to 6 post-randomization, the investigator will select the glimepiride dose based on clinical assessment. The guidance for glimepiride up-titration is outlined in [Section 3.3.2.1](#). If subjects meet up-titration criteria, a bottle of glimepiride, 4 mg, 6 mg or placebo, will be dispensed. If subjects do not meet up-titration criteria, subjects will continue the glimepiride prescribed to them at the previous visit. The up-titration of glimepiride dosing can occur before the scheduled study visits in the case of persistent hyperglycemia.

Weeks 7 to 96

- From weeks 7 to 12, each subject will continue taking glimepiride prescribed to them at week 6.
- At week 12 and at every 12 weeks of treatment thereafter, each study subject will receive 1 bottle of glimepiride capsules, 2mg, 4 mg, 6 mg or placebo, based on the kit number

assigned to the subject by the IWRS. At visit V15, two bottles of glimepiride capsules will be dispensed for dosing between week 72 and week 96.

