5.5. PROTOCOL DEVIATIONS

Protocol deviations will be captured during monitoring visits and recorded in CRF. Deviation will be classified into each of the 9 categories: enrollment criteria, non-compliance, laboratory, dosing, visit schedule, visit/procedure requirement, concomitant medication, informed consent, and other. Date and details of the deviation will be recorded. The list of deviation will be reviewed before unblinding and major protocol deviations that, in the opinion of the medical monitor, will be determined in the ongoing bases. The list of major protocol deviations will be further reviewed before database lock in the unblinded fashion and the deviations that could affect the primary and secondary variables will be determined. Some possible types of major protocol deviations are showing in Table 2.

Table 2 Some Possible Types of Major Protocol Deviations That Lead to Subject or Visit Exclusion from PP analysis set.

Category	Criteria	Exclusion
Inclusion/Exclusion Criteria		
Ineligible subject is enrolled	
 - Subjects not satisfying HbA_{1c} inclusion criteria - Subjects not satisfying eGFR inclusion criteria (inclusion #4 and #7) - Treated with SGLT2 within 3 months of screening 	Subject exclusion
Prior or Concomitant Medication Restrictions		
Use of another SGLT2 inhibitor	Use of an SGLT2 inhibitor, sulfonylurea, or additional metformin as the rescue medication for hyperglycemia	Visit exclusion [exclude data post rescue medication starts]
Randomization/Blinding		
Unblinding	Blind was broken (requested in IWRS)	Visit exclusion [exclude data post blind broken]
Dosing and Compliance		
Dosing Non-Compliance	Subject missed more than 20% of the investigational product doses for the 60 weeks of efficacy assessment period or missed more than 50% between week 48 and week 60	Subject exclusion

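### Unreturned glimepiride bottles that were replaced at up-titration are credited as 90 doses taken after about 14 to 42 days of use, which inflates glimepiride compliance and total dose

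*SAP*

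**What the plan says.** **Supply.** Both products come in bottles of 90 and are taken once daily. Protocol 5.9.2: "One bexagliflozin kit contains a bottle of 90 counts of bexagliflozin tablets, 20 mg or placebo". Protocol 5.9.3: "One glimepiride kit contains a 90 count bottle of one of the following products". Bexagliflozin is replaced every 12 weeks (Protocol 6.13.1): "At randomization and at every 12 weeks of treatment thereafter, each study subject will receive 1 bottle of bexagliflozin tablets". Glimepiride starts with one bottle at randomization, and further bottles may follow at weeks 2, 4 and 6 (Protocol 6.13.2): "If subjects meet up-titration criteria, a bottle of glimepiride, 4 mg, 6 mg or placebo, will be dispensed". The placebo capsules in the bexagliflozin arm go through mock titration on the same criteria (Protocol 3.3.2.1).

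**Counting.** SAP 9.2 sets doses taken equal to dispensed minus returned. For subjects who finish the study: "If subjects completed the study, all the unreturned bottles will be assumed to be completely consumed". For subjects who discontinue, bottles from any visit before the last are treated the same way. SAP 9.1 has the matching rule for total dose: "For unreturned bottles, if subject has completed the study, all study medications are considered as completely taken". The compliance denominator is daily doses times exposure days, with "Number of exposure days = last dose date - first dose date + 1". Compliance is summarized only for the non-placebo product, and one planned category is above 120%.

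**Per-protocol rule.** SAP 5.5, Table 2, lists as a reason for exclusion: "Subject missed more than 20% of the investigational product doses for the 60 weeks of efficacy assessment period". A second limb covers more than half of the doses missed between weeks 48 and 60. The table gives no formula and does not name the product to be counted.

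**The concern.** The crediting rule suits a bottle that lasts about as long as the interval it covers. A bexagliflozin bottle holds 90 tablets for 84 days, so assuming it was emptied overstates a full adherer by 6 doses. A glimepiride bottle replaced at week 2 has had 14 days of scheduled use, and crediting it with 90 doses is impossible on a once-daily regimen. The SAP has no exception for this case.

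Two outputs take the error directly: the compliance table and the glimepiride total dose. A third may do so. If the 20% rule in SAP Table 2 is programmed from the 9.2 count, some subjects who missed well over 20% of their capsules would stay in the per-protocol set. Protocol 9.5.2 treats agreement between the ITT and per-protocol results as strengthening a non-inferiority conclusion, so the make-up of that set matters even though it is secondary.

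**Working it through.** The plan states no figure for this overcount, so there is none to reproduce. The sample size (172 evaluable, 210 randomized per arm) does not enter.

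**Inputs.** Bottle size 90 (Protocol 5.9.2, 5.9.3). One dose a day of each product. Titration visits at weeks 2, 4 and 6 (Protocol 3.3.2.1). Bexagliflozin bottle interval 84 days (Protocol 6.13.1). Sixty weeks = 420 doses; 96 weeks = 672 doses. A pass on the first limb of SAP Table 2 needs 0.80 × 420 = 336 doses.

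**1. Excess credit per unreturned titration bottle** = 90 − days of scheduled use.

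| First bottle replaced at | Days used | Excess doses | Share of 420 |
|---|---|---|---|
| Week 2 | 14 | 76 | 18.1% |
| Week 4 | 28 | 62 | 14.8% |
| Week 6 | 42 | 48 | 11.4% |
| Two 14-day bottles | 28 | 152 | 36.2% |
| Bexagliflozin bottle, for comparison | 84 | 6 | 1.4% |

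**2. Compliance table (SAP 9.2 as written, 96-week completer).** A fully adherent glimepiride subject with two unreturned 14-day bottles scores (672 + 152)/672 = 122.6%, in the above-120% category. With one such bottle the score is (672 + 76)/672 = 111.3%. In each case 76 doses per bottle are also added to total dose under SAP 9.1.

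**3. Per-protocol rule, if computed from this count on active product over 420 days.** Let c be true adherence, assumed constant, k the number of unreturned bottles and u the days those bottles were in use, with all other bottles returned and counted correctly. Then

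counted compliance = [90k + c(420 − u)]/420.

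At c = 70%:
- Glimepiride, one 14-day bottle: (90 + 0.70 × 406)/420 = 374.2/420 = 89.1%, kept.
- Bexagliflozin, one 84-day bottle: (90 + 0.70 × 336)/420 = 325.2/420 = 77.4%, excluded.
- Bexagliflozin, two bottles: (180 + 0.70 × 252)/420 = 356.4/420 = 84.9%, kept.
- Nothing unreturned: 70% in either arm, excluded.

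At c = 75%, one unreturned bexagliflozin bottle gives (90 + 0.75 × 336)/420 = 342/420 = 81.4%, kept.

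The lowest true adherence that passes the first limb with one bottle unreturned is (336 − 90)/(420 − u). This is 60.6% for glimepiride replaced at week 2, 62.8% at week 4, 65.1% at week 6, and 73.2% for bexagliflozin. Titration bottles do not affect the weeks 48–60 limb.

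**4. With the credit capped at days in use (c = 70%).** Glimepiride, one 14-day bottle: (14 + 284.2)/420 = 71.0%, excluded. Bexagliflozin, one bottle: (84 + 235.2)/420 = 76.0%, excluded.

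**The case against.** **The affected group is narrow.** It needs an up-titrated subject whose replaced bottle never comes back. Subjects must bring all product to each visit and unused drug must be returned (Protocol 5.8, 5.11). Used medication is collected at weeks 2, 4 and 6, if applicable (Protocol 7.3.2 to 7.3.4). Gross overcounts would show in the above-120% category and the accountability listing. This limits the frequency, which the documents do not give. It does not make the stated rule correct.

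**The link to the per-protocol set is an assumption.** SAP Table 2 does not cite 9.2, offers its entries as possible types of deviation, and leaves major deviations to the medical monitor and a review before lock. This stands, so the figures in step 3 are conditional. They also depend on the denominator. Over 672 days the same 70% adherer scores (90 + 0.70 × 658)/672 = 81.9% on glimepiride and (90 + 0.70 × 588)/672 = 74.6% on bexagliflozin, while a 65% glimepiride adherer scores (90 + 0.65 × 658)/672 = 77.0% and is not lifted past 80%.

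**Three stronger readings are tempting but not supported.**
- *Glimepiride non-compliers pass and bexagliflozin non-compliers do not.* The rule covers tablets too. A bexagliflozin subject passes at 75% adherence with one unreturned bottle and at 70% with two. Comparing 76 excess doses with 6 also exaggerates the contrast, because the 6 assumes a full adherer. For a 70% adherer the gain is 19.1 points on glimepiride and 7.4 on bexagliflozin.
- *The per-protocol comparison is therefore biased towards non-inferiority.* The restriction to non-placebo product in 9.2 concerns the summary table. SAP Table 2 speaks of investigational product without that limit. If both products are counted, mock titration gives the bexagliflozin arm the same extra bottles. No shift in HbA1c can be derived from the documents.
- *The exposure-day denominator lets a subject who stops at week 10 into the per-protocol set.* Such a subject can score 100% under 9.2, but SAP Table 2 has its own 60-week base. There, 70/420 = 16.7% taken fails the first limb, and no doses in weeks 48–60 fails the second.

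**Conclusion.** The defect in SAP 9.1 and 9.2 is real and follows from the text. An unreturned titration bottle is over-credited by 48 to 76 doses at scheduled visits, and two 14-day bottles by 152. An early unscheduled up-titration could shorten the use further. In the compliance table and the glimepiride total dose, the titration overcount falls on the glimepiride arm, because only active product is reported there. It can make a fully adherent subject look over-dosed (122.6%).

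The effect on the per-protocol set is possible but not established. It needs the 9.2 count to drive SAP Table 2, active product only, and constant adherence with all other bottles correctly counted. Even then the arms differ in degree. SAP Table 2's silence on formula and product is a gap that needs closing in any case.

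The number of subjects affected cannot be stated without a non-return rate. The non-inferiority test rests on the ITT set (SAP 8.1.1) and is unaffected. This is a correction to make before lock, not a threat to the trial's main conclusion.

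**What to change.** - **SAP 9.1 and 9.2:** cap the doses credited to any unreturned bottle at the days from its dispensing to the dispensing of its replacement, or to last dose if there was none. Treat two bottles dispensed together as one unit for the cap.
- **SAP Table 2:** state that missed doses are counted on the active product in each arm, with this capped count, over scheduled Days 1–420.
- **Reconcile** SAP 9.2, which refers to two bottles dispensed at week 60 or week 72, with Protocol 6.13, which has two bottles at week 72 only.

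The cost is a few lines of SAP text and a small programming change. SAP 9.2 already credits by date when a discontinued subject's last bottles are missing, so the method and the dates exist. The cap does not cure non-return: it still assumes full daily use of a missing bottle, and a 70% bexagliflozin adherer with two missing bottles would count as (168 + 176.4)/420 = 82.0% and pass. Reporting unreturned bottles by arm would show whether this matters.
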